6.D.2. Visit 1 (Baseline Visit): N= 160 subjects will be randomly assigned to receive either ZNS (80 subjects) or placebo (80 subjects). We will use blocked stratified randomization with treatment site (VA Connecticut versus Bedford) and the use of other psychotropic medications (e.g., antidepressants) as the stratification variables, with block sizes of 4 in each stratum to achieve treatment balance throughout the randomization process. Within 21 days after the screening visit, eligible subjects undergo a two-hour pre-treatment assessment (described below). At the baseline visit, subjects will complete a packet of questionnaires. Subjects will receive their first medication management session and first supply of study medication during a treatment session (visit 1) scheduled on the same day, following completion of the baseline assessments.

Subjects will begin study medication (i.e., ZNS or matching placebo) at an initial dosage of 100mg/day. All subjects will be asked to bring any remaining capsules and the study medication container to their next and all subsequent clinic visits, so that capsule counts can be used to measure compliance. The subject begins 6-week titration phase, during which the dosage will be titrated up as indicated above and in Table 1. Subjects will be paid a nominal but fair amount of money in compensation for all visits, including follow-up visits. Table 1 shows the titration schedule:

TABLE 1: Medication Titration Schedule

Week	Placebo	Zonisamide dose
1	One capsule daily	100mg QHS
2	Two capsules daily	200mg QHS
3	Two capsules daily	200mg QHS
4	Three capsules daily	300mg QHS
5	Three capsules daily	300mg QHS
6	Four capsules daily	400mg QHS
7	Four capsules daily	400mg QHS
8-9	Five capsules daily	500mg QHS (Target dose)
10-16	Five or Six capsules daily, 7 weeks duration	Continue 500mg daily or optional increase to 600mg QHS, 7 weeks duration
17-18	TAPER: Decrease capsules by one a day every 3 days, over a period of up to 15 days	TAPER: Decrease dose 100mg every 3 days, over a period of up to 15 days

Table 1 notes: 7 weeks of titration to the 500mg daily target dose. 9 weeks at the target dose with the option to increase to 600mg daily after two weeks at target if treatment response is suboptimal and there are no significant side effects (no current moderate to severe AE's with 500mg daily).

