We will use the percentage of subjects with no heavy drinking days (**PSNHDD**) as the primary outcome variable. This outcome is the FDA recommended endpoint for pivotal trials, and is described in Falk et al., (2010). The PSNHDD can be derived from each subject's TLFB data. An important initial consideration in considering effectiveness will be to identify baseline differences between groups that may have occurred despite randomization. **Successful outcomes during the treatment trial will be defined in terms of a statistically significant difference on the primary outcome measure: PSNHDD, compared during the 8 weeks of active treatment at the target dose, allowing for a 6 week grace period for the medication titration.** For all analyses, heavy drinking days will be defined as follows; for men > 5 drinks in a day and for women > 4 drinks in a day. Patients will be followed irrespective of whether they continue to receive medication treatment, so that analysis will include all data available for the 8-week treatment period. The analysis will be **intent-to-treat**, and dropouts will be considered as having relapsed to heavy drinking. We will use a logistic regression analysis with PSNHDD as a categorical dependent variable. Medication condition (placebo or ZNS) will be the main independent variable, and we will include the variables of early onset of alcoholism (EOA, binary), and the use of additional psychotropics (e.g., antidepressants, a binary variable) as covariates. The α will be set at .05 for the primary outcome variable. Between site differences will be explored.

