All secondary outcome analyses will be by intention to treat, a conservative approach that is aimed at avoiding an overestimation of the treatment effect and will include all subjects that take any medication and provide drinking data for at least one week. The use of multilevel repeated measure statistical models may increase the study power and potential to detect a treatment effect. This type of repeated-measures analysis 1) provides missing-data imputation procedures that are both conservative and logical; 2) allows for the measurement of the exact time that a given patient is measured at baseline and follow-up points, which need not be the same among patients; 3) plots and analyzes linear and non-linear time-course functions both overall and for subgroups of patients based on each patient's best estimate linear and non-linear regression line plots. We will use all available data on individuals and thus dropouts provide data until the point of dropout. The best-fitting variance-covariance structure between the repeated measures will be selected based on Schwartz-Bayesian Information Criterion (BIC). We will compare dropout patterns between groups and if there are concerns of informative dropout and/or informative intermittent missing data, we will use pattern mixture models (Hedeker and Gibbons, 1997) to perform sensitivity analyses to our main analyses. Adherence to the medication will be evaluated and factored into the analysis. We will evaluate and compare both medication conditions (placebo, ZNS) for percentage of prescribed pills taken. We do not expect a difference, but if one is found, we can then perform additional analysis on the main outcome variables to estimate treatment effects adjusted for percent pills taken. The number of MM sessions attended will be recorded and analyzed similar to the medication adherence.

The three-month follow up data will be gathered using a retrospective TLFB at the follow-up time point, and will be analyzed using logistic regression for PSNHDD, and either linear mixed models or Hierarchical Linear Modeling (HLM) for other outcomes. We will examine that drinking data between the end of treatment and the three-month time point and use the same outcomes as the main analysis. We will be able to examine for persistent effects of ZNS on drinking behavior and related outcomes. These analyses will include pre-treatment and within-treatment drinking data as covariates to evaluate the post-treatment effects of ZNS.

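### The optional adherence analysis adjusts the treatment effect for percent pills taken, a post-randomisation variable, and is triggered by the arm difference that makes the adjusted effect biased

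*Combined protocol and SAP*

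**What the plan says.** The adherence text is in section 6.I.2 of the combined protocol and SAP, in the discussion of the secondary outcome models. It opens with a firm but unspecific statement: "Adherence to the medication will be evaluated and factored into the analysis". It then sets a comparison: "We will evaluate and compare both medication conditions (placebo, ZNS) for percentage of prescribed pills taken". The next step is conditional and optional: "We do not expect a difference, but if one is found, we can then perform additional analysis on the main outcome variables", the purpose being to "estimate treatment effects adjusted for percent pills taken". MM attendance follows the same path: "The number of MM sessions attended will be recorded and analyzed similar to the medication adherence".

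Pill-taking is measured during treatment. Section 6.D.2 has subjects return containers and unused capsules at every visit, "so that capsule counts can be used to measure compliance".

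The main analyses are separate from this. The primary PSNHDD (percentage of subjects with no heavy drinking days) analysis in 6.I.2 is an ITT logistic regression whose listed covariates are early onset and use of other psychotropics, and "dropouts will be considered as having relapsed to heavy drinking". For the rest, "All secondary outcome analyses will be by intention to treat".

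The documents give no threshold for a difference in pill-taking, no estimand for the adjusted effect, no caveat that adherence arises after randomisation, and no causal method for it.

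**The concern.** Randomisation makes the arms comparable at baseline. It does not make patients with the same pill count comparable if the drug itself changes who takes pills. Suppose ZNS lowers adherence through side effects, and patients with a better prognosis both take more pills and drink less. A ZNS patient at 80% of pills is then, on average, a better-prognosis patient than a placebo patient at 80%. Holding pills fixed credits that difference in prognosis to the drug.

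The documents make both links plausible without establishing either:

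- **Drug to adherence.** Section 4.A.3 names side effects as a barrier to medication treatment, and suggests that weight loss on ZNS may help adherence. A gap could go either way.
- **Drinking to adherence and attendance.** Under 6.D.4, subjects who request or clearly need more alcohol treatment may be discontinued from the protocol. Under 6.E.1, missing consecutive visits can lead to withdrawal. Dropouts are then scored as relapsed. MM attendance is tied to the assigned outcome in this way, and so is pill-taking if the percentage is taken over the full course, which the plan does not specify.

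At stake is a supportive estimate, on the main outcomes, that could be presented as the drug effect corrected for adherence and could differ from the ITT result for reasons unrelated to the drug.

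**Working it through.** **The plan's own figure.** The adherence text carries none. The nearest is the PSNHDD power in 6.I.6. Taking the pilot counts of 12 and 7 over an assumed 20 per arm (pilot N = 40) gives 60% and 35%. With 80 per arm and two-sided 0.05 (sidedness is not stated), the null SE is √(2 × 0.475 × 0.525/80) = 0.0790 and the alternative SE is √((0.24 + 0.2275)/80) = 0.0764. Then z = (0.25 - 1.96 × 0.0790)/0.0764 = 1.246 and power is 89.4%, which matches the stated figure of over 89%. The 35% is reused below as the placebo rate.

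**Continuous outcome (such as drinks per week), closed form.** From the documents: 80 per arm and alpha 0.05. Assumed: no drug effect, ZNS adherence lower by g within-arm SDs, and within-arm correlation r between pills and drinking.

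- Adjusted effect in SDs of drinking = 0 - r × (-g) = r × g. Negative values favour ZNS.
- SE = √[(1 - r²)/(40 × (1 - R²))], where 40 = 160 × 0.25 and R² = (g²/4)/(1 + g²/4).
- Type I error = P(Z > 1.96 - |effect|/SE) + P(Z < -1.96 - |effect|/SE).

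| g | r | Adjusted effect | SE | Type I error |
|---|---|---|---|---|
| 0.5 | -0.3 | -0.15 | 0.156 | 16.2% |
| 0.5 | -0.5 | -0.25 | 0.141 | 42.5% |
| 0.31 | -0.3 | -0.093 | 0.153 | 9.4% |
| 0.31 | -0.1 | -0.031 | 0.159 | 5.4% |

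The gap of 0.31 SD is the smallest that would just reach p = 0.05 in the arm comparison: 1.96 × √(2/80) = 0.310. Simulations of 4,000 trials at g = 0.5 gave 16% to 17% (r = -0.3) and 41% to 42% (r = -0.5), against about 5% unadjusted. If ZNS adherence is 0.5 SD higher instead, the effects become +0.15 and +0.25 SD.

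**Chance of triggering.** Assuming a t-test at 0.05, a true 0.5 SD gap gives z = 0.5/√(2/80) = 3.16, and the adjustment is triggered in about 88% of trials.

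**Binary outcome (PSNHDD), simulation.** All inputs except N are assumed. Placebo PSNHDD is 35%. An unmeasured prognostic factor adds 12 points of adherence and 1.0 in log-odds of response per SD. Placebo adherence is centred at 85% with further random spread, lowered on ZNS by the gap shown, then capped to 0–100%. Odds ratios and risk differences come from 400,000 subjects, and error rates from 4,000 trials of 160.

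No drug effect:

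| Gap (points, before capping) | ITT odds ratio | Adjusted odds ratio | Adjusted risk difference | ITT error | Adjusted error |
|---|---|---|---|---|---|
| 0 | 0.98 | 0.98 | -0.004 | 5.0% | 5.0% |
| 5 | 1.00 | 1.19 | 0.037 | 4.9% | 7.8% |
| 10 | 1.00 | 1.43 | 0.074 | 5.2% | 16.3% |
| 20 | 1.01 | 2.13 | 0.155 | 4.7% | 42.8% |

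With a true effect that scales with pills taken, the ITT risk difference at zero gap is 0.211 and the adjusted one 0.210. At gaps of 5, 10 and 20 points, ITT gives 0.198, 0.187 and 0.161, while adjustment gives 0.241, 0.272 and 0.331. The ITT effect falls as adherence falls, but the adjusted effect rises above its zero-gap value.

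The two models agree: there is no distortion without a gap, and it grows as the gap widens.

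**The case against.** The strongest reply concerns status. The step is optional, conditional and additional. Success on the primary outcome rests on the ITT logistic regression, which does not include pills, and the secondary outcomes are ITT as well. A reader might infer that the adjusted estimate replaces or overrides the randomised comparison. The documents do not support that. The one firm sentence, that adherence will be factored in, names no method, and the sentences after it spell it out as an optional step. This part of the objection stands and limits the point to a supportive analysis.

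Second, the inputs are assumed. The plan expects no difference in pill-taking, and sections 2 and 8.B aside, its background describes ZNS as well tolerated in the pilot. No document gives a gap, a correlation or a direction, so the 42% is the upper end of a chosen range. That stands.

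Third, a difference can arise by chance. Then the adjustment does little harm: at zero true gap its error was 5.0% overall and 6.5% among the roughly 200 of 4,000 trials that triggered it, which is within simulation error of 5%. So an observed difference does not prove that treatment changed adherence. But the plan has no means of telling the two cases apart, and a real gap triggers the analysis far more often than chance does.

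Fourth, the MM sentence may mean only a by-arm comparison. That reading is open, and no magnitude was calculated for MM. Since adjustment is part of how pill adherence is handled, the sentence permits it.

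Finally, it could be enough to label the analysis exploratory. That would reduce misreading but not bias. The Bonferroni correction planned in 6.I.2 does not remove bias either.

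**Conclusion.** The point holds as a flaw in a supportive analysis. Covariate adjustment for percent pills taken, or for MM sessions, does not estimate a treatment effect on the main outcomes when treatment has shifted those variables and they share causes with drinking within arm. The trigger selects for the first of these conditions. There would be no such bias if pills taken were unrelated to drinking given arm.

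Under the assumed inputs (no drug effect, 80 per arm, ZNS adherence 0.5 SD lower, r from -0.3 to -0.5), the adjusted estimate favours ZNS by 0.15 to 0.25 SD, with type I error of about 16% to 42%. A gap of 0.31 SD brings the error down to about 9% at r = -0.3 and 5% at r = -0.1. Higher adherence on ZNS would turn the bias against the drug.

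The documents do not support saying that the trial's conclusions will be biased, that ZNS will be favoured, or that the ITT results are compromised.

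**What to change.** In section 6.I.2:

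1. Remove the covariate adjustment for percent pills taken, and state that MM sessions will not be used as an adjustment variable either.
2. State that the ITT estimate is the treatment effect, and replace the general sentence about factoring adherence into the analysis with what will actually be done.
3. Keep the by-arm comparison of pill-taking and MM attendance that is already planned, reported as outcomes in their own right.
4. If an adherence-related effect is wanted, pre-specify its estimand and a method that uses randomisation as the instrument for pill-taking. State the assumptions: assignment affects drinking only through pills taken; either a definition of complier or a linear dose-response for a continuous pill percentage; and how dropouts scored as relapsed enter, since early stoppers may have both few pills and an assigned outcome.

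Items 1 to 3 cost SAP wording and use the same data. Item 4 needs no new data, but its intervals will be wider than the ITT intervals and its assumptions cannot be fully checked.

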Specific Aim 1 (Primary Aim): To determine the effectiveness of ZNS treatment in reducing drinking on the primary outcome measure: drinks per week (measured using the Timeline Followback Method), for eight weeks at a target dose of 600 mg of ZNS daily for 160 heavy-drinking, alcohol-dependent veterans. We hypothesize that ZNS treatment will reduce the heavy drinking days per week and the total drinks per week significantly more than the placebo and that the benefits will persist at three months follow-up after treatment.

Specific Aim # 2 (Secondary Aim): To examine the effects of ZNS treatment on heavy drinking days per week, , percentage of subjects with no heavy drinking days (PSNHDD) the urge to drink (craving), biomarkers of alcohol intake, clinical global impression, medication tolerability, and other patient-centered outcomes. We hypothesize that ZNS will demonstrate significantly greater improvements than the placebo on these measures by the treatment endpoint as well as at follow-up.

Specific Aim #3 (Secondary): To use telephone-based daily process data collection to elucidate the mechanism of action of ZNS as it relates to changes in craving, anxiety, and genetic variation. *This method has been shown to elucidate the mechanism of action of topiramate, as well as its pharmacogenetic interactions.* We hypothesize that ZNS' effects will be moderated by genetic variation, craving, and anxiety, but mediated through changes in self-efficacy to reduce heavy drinking.

Specific Aim #4 (Exploratory): The exploratory aim is to examine the pharmacogenetic interactions between ZNS and the therapeutic response. We hypothesize that both the long (L) allele of the VNTR polymorphism in exon 3 of the *DRD4* gene and the CC genotype of the *DBH* rs1611115 (C-1021T) SNP will show a pharmacogenetic effect with ZNS, as evidenced by a greater reduction in drinking than for the short (S) allele and T carriers respectively.

Specific Aim #5 (Exploratory) To compare ZNS and placebo-treated subjects on pre- and post-treatment changes in measures of stress-reactivity (i.e., stress-induced anxiety, alcohol craving, autonomic nervous system activity), cue-elicited craving, and impulsivity. We hypothesize that ZNS will attenuate stress-reactivity, cue-elicited craving, and impulsivity more than placebo in a stress laboratory paradigm, and that attenuation of those measures will be associated with reduction in drinking.

4. BACKGROUND:

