6.D.6. Visit 18 (Tapering Medication Checkup): *This occurs two weeks after the endpoint visit (see TABLE 3 below in section #8).* Study medication will be tapered off over approximately 2 weeks. ZNS (or placebo) will be reduced by 100mg every three days until stopped. Subjects will be asked to return to the clinic 2 weeks after the endpoint assessment to assess successful tapering of study medication.

6.D.7. Three Month Follow-up Visits (Visit 19): Subjects will be asked to return at 3 months after the acute 16 week treatment phase is ended, to assess the enduring effects of medication treatment. They will complete TLFB, measures of mood, quality of life, alcohol use disorder symptoms, health symptoms, and blood will be drawn for biomarkers of alcohol use.

6.E. Study Treatments:

6.E.1. Pharmacotherapy Conditions. The medication will be administered as described above. Subjects who have unacceptable side effects or severe psychological symptoms (e.g., suicidal thoughts strong enough to suggest the subject can't be managed safely in the outpatient setting) will be withdrawn from the study.

Subjects will also be withdrawn from the study if they opt to discontinue it, become pregnant, or violate study rules (e.g., fail to attend two consecutive visits).

6.E.3. Medical Management (MM): This is a manual-based minimal behavioral psychosocial intervention that has been used effectively in previous clinical trials to optimize adherence to medication and treatment goals (12, 68). MM helps patients stay focused on treatment goals and on taking the medication, and will take about 20 minutes per appointment, at each appointment. This intervention will help reinforce treatment goals, and allow for a therapeutic interaction with patients on placebo. MM does not include more intensive therapeutic techniques such as those used in Cognitive Behavioral Therapy (CBT). The use of MM will facilitate the evaluation of the medication effect. We will use a modified version that allows for subjects to have a goal of abstinence or non-hazardous drinking.

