We will use a mixed models approach to examine **secondary outcome measures (Specific Aim 2)** for a statistically significant difference in; drinks per week, and heavy drinking days per week, the outcomes used in the pilot study. The model will include fixed effects for medication group, week, and the interaction between medication and week, also controlling for pre-treatment drinking behavior data, and using a random effect for intercept. We will incorporate a grace period corresponding to the time it takes to titrate the medication to target dose into the models, and we will focus the primary analysis on the 8 weeks of treatment at the target dose. Aggregate outcome measures such as the percentage of heavy drinking days, which can be examined using several different methods, will be considered. A statistically significant difference on any of the secondary measures of both heavy drinking and drinking, with clinically significant effect sizes, will be considered a relative success for the medication. Additional secondary outcome measures will include changes in GGT level, measures of alcohol urge or craving to use (AUQ), measures of depression and anxiety, measures of physical health and quality of life (Q-LES-Q, the and the RAND-36) and level of alcohol-related problems (as measured on the SIP). These can also be performed with the mixed models approach. Statistical models evaluating time to relapse, drinking trajectories, percentage of abstinent days, drinks per drinking day, and total abstinence rates will be considered. **We will use the Bonferroni correction for the secondary outcomes and additional comparisons to guard against chance findings.**

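### The only three-month follow-up models specified adjust for on-treatment drinking, so persistence of benefit is not tested and, if ZNS works as hypothesised, would be understated

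*Combined protocol and SAP*

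**What the plan says.** Four places say what the three-month data are for.

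- Specific Aim 1 (Section 3) hypothesises that "the benefits will persist at three months follow-up after treatment".
- Specific Aim 2 expects "significantly greater improvements than the placebo on these measures by the treatment endpoint as well as at follow-up".
- Section 6.D.7 schedules Visit 19 "to assess the enduring effects of medication treatment".
- The follow-up paragraph of Section 6.I.2 states: "We will be able to examine for persistent effects of ZNS on drinking behavior and related outcomes".

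That paragraph is also the only place where a follow-up analysis is specified. It names logistic regression for PSNHDD and linear mixed models or HLM for the other outcomes. It then sets the covariates for all of them: "These analyses will include pre-treatment and within-treatment drinking data as covariates to evaluate the post-treatment effects of ZNS". It does not say whether within-treatment drinking enters as a yes/no PSNHDD status or as an amount.

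The on-treatment models in the same section are different. For the PSNHDD logistic model, "we will include the variables of early onset of alcoholism (EOA, binary), and the use of additional psychotropics" are the covariates. The mixed models for drinking are described as "also controlling for pre-treatment drinking behavior data, and using a random effect for intercept".

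**The concern.** The aims describe a comparison of the randomised arms at follow-up. Within-treatment drinking lies between randomisation and that comparison, and Aim 1 predicts that ZNS changes it. Conditioning on it removes the part of the follow-up difference that on-treatment drinking already predicts. What remains is an incremental effect. That is a legitimate question, but it is not whether the benefit persists.

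A real and lasting benefit could therefore be reported as one that did not persist. If the benefit fades faster than on-treatment drinking predicts, the coefficient could favour placebo while ZNS subjects are still doing better. No follow-up model without the covariate is planned to set against that result.

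**Working it through.** **1. The plan's own figure.** Section 6.I.6 gives power above 89% for on-treatment PSNHDD with 80 per arm, from pilot counts of 12 and 7. Taking 20 per arm in the pilot of 40 (the split is an assumption), the rates are 0.60 and 0.35, with mean 0.475.

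- SE under the null = √(2 × 0.475 × 0.525 / 80) = 0.0790
- SE under the alternative = √((0.24 + 0.2275) / 80) = 0.0764
- Power, two-sided 0.05 = Φ((0.25 − 1.96 × 0.0790) / 0.0764) = 0.894

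The figure reproduces. It concerns the treatment period; the plan gives no rate, effect size or power for follow-up.

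**2. A case that can be done by hand.** Suppose the chance of follow-up success depends only on on-treatment status, say 0.7 after success and 0.1 after failure (assumed), in both arms.

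- ZNS: 0.60 × 0.7 + 0.40 × 0.1 = 0.46
- Placebo: 0.35 × 0.7 + 0.65 × 0.1 = 0.31
- Odds ratio between arms: (0.46/0.54) / (0.31/0.69) = 1.90
- Odds ratio given on-treatment status: 1.0

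The arms differ by 15 percentage points at follow-up, and the planned model has nothing left to find.

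**3. Linear outcome.** Let the on-treatment benefit be D, the share persisting at follow-up f, and the within-arm slope of follow-up on on-treatment drinking b. Then

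adjusted effect = fD − bD = D(f − b).

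On the latent scale D = Φ⁻¹(0.60) − Φ⁻¹(0.35) = 0.253 + 0.385 = 0.639 SD.

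- f = 1: the effect is 0.64 without the covariate, and 0.45 (b = 0.3) or 0.19 (b = 0.7) with it.
- f = b: the adjusted effect is zero.
- f = 0.5, b = 0.7: the effect is 0.32 without the covariate and −0.13 with it.

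The sign reverses whenever f is below b.

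**4. PSNHDD by simulation.** All values here are assumed. Within-arm SD is 1. On-treatment drinking is 0.4 × baseline − 0.639 for ZNS + error. Follow-up drinking is b × on-treatment + 0.1 × baseline − 0.639(f − b) for ZNS + error. Success is falling below the cut-off that gives 35% on placebo. There is no unmeasured common cause. Odds ratios come from 1,000,000 subjects, and every model includes baseline:

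| f | b | No covariate | Binary covariate | Level covariate |
|---|---|---|---|---|
| 1 | 0.3 | 2.90 | 2.46 | 2.20 |
| 1 | 0.5 | 2.96 | 2.27 | 1.89 |
| 1 | 0.7 | 3.08 | 2.12 | 1.62 |
| 0.5 | 0.5 | 1.73 | 1.26 | 1.01 |
| 0.5 | 0.7 | 1.77 | 1.04 | 0.72 |
| 0.25 | 0.5 | 1.31 | 0.92 | 0.73 |

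Power for f = 1 (160 subjects, 3,000 trials, two-sided 0.05, no dropout):

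| b | No covariate | Binary covariate | Level covariate |
|---|---|---|---|
| 0.3 | 0.91 | 0.75 | 0.62 |
| 0.5 | 0.91 | 0.61 | 0.39 |
| 0.7 | 0.92 | 0.50 | 0.22 |

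Section 6.I.2 also states: "We will use the Bonferroni correction for the secondary outcomes and additional comparisons to guard against chance findings". It does not give the number of tests. If five are assumed (level 0.01), power of about 0.75 falls to 0.53–0.26 (binary) or 0.37–0.08 (level).

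**5. Checks.** A simpler latent model without baseline, with a binary covariate and correlations of 0.3, 0.5 and 0.7, takes the odds ratio from about 2.8 to 2.40, 2.17 and 1.98, and power from 0.88–0.89 to 0.74, 0.60 and 0.44. If ZNS has no on-treatment effect (total follow-up effect 0.32, b = 0.5), nothing is attenuated: the linear effect stays at 0.319 and the odds ratio moves from 1.72 to 1.83 or 1.89.

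**The case against.** **The incremental effect may be what was wanted.** The covariate sentence gives post-treatment effects as its purpose, and that is a coherent question. This stands as a reading of the sentence. It still leaves the persistence hypotheses of Aims 1 and 2 with no analysis. Where the plan does want mediation, for self-efficacy in Section 6.I.4, it sets out an explicit approach; the follow-up paragraph has none.

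**The plan adjusts for post-randomisation variables elsewhere.** Section 6.I.2 allows adjustment for percent of pills taken, and other psychotropics may be used during the study. But the pill adjustment is an additional analysis to be run if the arms differ, and psychotropic use is a randomisation stratum in Section 6.D.2. The contrast with the main on-treatment models holds.

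**The illustrations lean towards the worst case.** This is partly right. The fall from 0.91 assumes full persistence. In the same model, power without the covariate is only about 0.67 at f = 0.75, 0.36–0.39 at f = 0.5 and 0.13 at f = 0.25, so dropping the covariate does not guarantee a well-powered follow-up test. In the two sign-reversal rows, the level-adjusted model is significant at 0.05 in only about 11–13% of trials. A false null is therefore the realistic risk; a significant result against ZNS is less likely.

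**Follow-up is not the success criterion.** That is correct. Section 6.I.2 defines success on PSNHDD during treatment, which this does not touch.

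**Conclusion.** The concern holds. As written, every three-month model conditions on a variable that treatment is expected to change, and none estimates the difference between randomised arms that Aims 1 and 2 and Section 6.D.7 describe. This follows from the text alone.

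The size depends on assumptions that the documents cannot settle: 60% against 35% on treatment, slopes of 0.3 to 0.7 and the share of benefit that persists. Within that range a persisting benefit is shrunk at every value tried, is removed on the linear scale when f equals b, and reverses when f is smaller. The unstated form of the covariate also matters: at f = b = 0.5 the odds ratio is 1.26 with the binary form and 1.01 with the level. Attenuation requires both an on-treatment effect of ZNS and a positive link between on-treatment and follow-up drinking. The change should be made, but the primary conclusion does not depend on it.

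**What to change.** Rewrite the follow-up paragraph of Section 6.I.2 before unblinding.

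- **Main persistence analysis, every follow-up outcome:** medication plus pre-randomisation covariates, without within-treatment drinking. Use pre-treatment drinking throughout; for PSNHDD add early onset and psychotropic use as in the primary model, taking psychotropic use as recorded at randomisation. For outcomes other than drinking, the outcome's own baseline value is a natural addition where it was measured.
- **Exploratory analysis:** keep the model with within-treatment drinking, label it as an incremental or mediated effect, and state whether the covariate is binary PSNHDD status or drinking level.
- **Interpretation:** state that conclusions about persistence rest on the main analysis only.

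The cost is SAP wording and one extra model per follow-up outcome. The TLFB data are already planned, so no visits, subjects or measures are added.
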